2.2 Key characteristics of the organisation and site

Healthy community participants will be recruited in Ndirande wards, which are under the Blantyre District Health Office. These wards are likely to be representative of the baseline community resistome for children admitted to QECH, due to the geographical proximity of this ward to the hospital. Community participants with pneumonia will be recruited in Ndirande health centre and GPCC, a primary care clinic near to QECH. Hospitalised participants will be recruited from QECH, a tertiary referral hospital in central Blantyre.

NP Resistome Study

Version 5.0 21/05/2025

Page 13 of 30

The Malawi Liverpool Wellcome Programme (MLW) was founded in 1995 and is a partnership between Kamuzu University of Health Sciences (KUHeS), LSTM and the University of Liverpool; core funding is provided by the Wellcome trust. MLW has modern ISO15189 accredited diagnostic laboratories, and dedicated laboratories for microbiology and molecular biology. MLW also has a dedicated clinical research pharmacy and runs several clinical sites around the country. MLW has also invested in a strategy for integrated data collection platforms, with robust management systems and transparent, safe and GCP-compliant data sharing, allowing clinical, researcher and collaborator data access.

2.3 Study population

The study population will be healthy children aged 12-24 months in Ndirande, children aged 12-24 months with pneumonia presenting to GPCC and children aged 12-24 months hospitalised with pneumonia at QECH. Children with severe anaemia (haemoglobin level < 70 grams per Litre), on long-term antibiotic treatment or prophylaxis, children on immunosuppressive medications or with an immunosuppressive illness, including HIV infection, will be excluded from the study.

2.4 Study period

This study will be conducted over a three-year period as a PhD fellowship, with participant recruitment over an 18-month period; see Figure 3. Due to the budget, our study team will not have the capacity to recruit in the community and hospital concurrently; community participants will be recruited prior to hospital participants.

We have chosen a 3-month follow up timepoint, to allow the resistome to return to a post-antibiotic baseline; a previous study demonstrated microbiome recovery within 3 months of infective-asthma exacerbation [23].

Importantly, there is evidence of seasonal variation in composition of the NPM and NPR [24]. Unfortunately, our study team size is restricted by budgetary constraints, therefore we are unable to recruit in the community and hospital simultaneously. We plan to conduct most of the community patient recruitment intensively within a 6-month period, before starting hospital recruitment. To restrict potential confounding due to seasonal effect, we plan to return to the community on an infrequent basis (approximately 3-4 weekly) for healthy community sampling over the following 6 months to ensure a baseline healthy resistome has been sampled across all seasons.

NP Resistome Study

Version 5.0 21/05/2025

Page 14 of 30

	December 2024 - February 2025	March - May 2025	June - August 2025	September - November 2025	December 2025 - February 2026	March - May 2026	June - August 2026	September - November 2026	December 2026 - February 2027	March - May 2027	June - August 2027
Set up study in-country											
Recruitment and data											
collection from COMMUNITY cohort											
Recruitment and data											
collection from											
HOSPITAL cohort DNA extraction and											
sequencing											
Bioinformatic pipeline											
optimisation											
Statistical analysis and thesis preparation											

Figure 3. Study timeline

Samples collected from study participants will be stored for 5 years after the conclusion of the study at Malawi Liverpool Wellcome program. The study will be completed within 18 months of the start of recruitment, or when the recruitment targets have been achieved and all samples collected (if this occurs in a time frame shorter than 18 months). Upon study completion, the Sponsor (LSTM), RECs and MLW will be notified; a report of the study findings will be submitted to COMREC, Blantyre district health office and LSTM.

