1.3.2 Primary Objectives

- To measure how the diversity and relative abundance of the nasopharyngeal resistome of children hospitalised with pneumonia differs from the nasopharyngeal resistome of healthy children in the community.
- To measure how the diversity and relative abundance of the nasopharyngeal resistome of children hospitalised with pneumonia differs from the nasopharyngeal resistome of children with pneumonia treated with antibiotics in the community.
- Investigate whether there is measurable persistence of a hospital-acquired nasopharyngeal
 resistome post-discharge, and whether this is associated with adverse health outcomes,
 including recurrent hospitalisation.

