2.9.1 Primary analysis

Participants will be gender-matched across groups. To establish differences in NPR composition the mean NPR diversity in a sample (measured using the Shannon index), mean relative abundance of all ARGs in a sample and mean relative abundance of specific ARGs in a sample will be compared between study groups using unadjusted t-tests, as summarised in Figure 4. Statistical analysis will be performed in R. Results will be presented in tables and illustrative heatmaps.

[figure not shown]

Figure 4. Plan for statistical analysis of NPR composition.

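### For hospitalised versus community pneumonia (primary objective 2), a seasonal shift in the resistome can appear as a hospital effect: recruitment is sequential, the seasonal remedy covers healthy children only, and the primary test is unadjusted

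*Protocol*

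**What the plan says.** Protocol section 2.4 states that "there is evidence of seasonal variation in composition of the NPM and NPR". For budget reasons the two settings cannot run together, so "community participants will be recruited prior to hospital participants". Recruitment is described as "with participant recruitment over an 18-month period", and on the community side: "We plan to conduct most of the community patient recruitment intensively within a 6-month period, before starting hospital recruitment".

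The remedy for season is a set of return visits, "approximately 3-4 weekly) for healthy community sampling over the following 6 months", whose purpose is "to ensure a baseline healthy resistome has been sampled across all seasons". No later recruitment of community children with pneumonia is described, and no pacing is set for the hospitalised group.

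The second primary objective (1.3.2) asks how the resistome of hospitalised children "differs from the nasopharyngeal resistome of children with pneumonia treated with antibiotics in the community". Under 2.9.1, groups are matched on gender only, and mean diversity and abundance "will be compared between study groups using unadjusted t-tests". The one adjusted model, in 2.9.2, concerns re-hospitalisation. Season is not among the confounders it gives as examples.

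**The concern.** Objective 2 is meant to separate the effect of hospital exposure and intravenous antibiotics from that of community antibiotic treatment. One arm is sampled mostly in a single six-month window and the other in a later period. If the resistome differs between the seasons the two arms represent, an unadjusted t-test attributes that difference to the hospital. A larger sample does not help, because the bias stays fixed while the standard error shrinks.

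The protocol names this threat and acts on it for the healthy group only. The order and pace of recruitment cannot be repaired after enrolment.

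**Working it through.** **Inputs from the protocol.** Two-sided 5% type I error, 90% power, standardised difference 0.505 and 83 per group (2.5). Recruitment lasts 18 months, with most community recruitment in the first 6 (2.4), so the hospital phase is about 18 − 6 = 12 months. That last figure is inferred, because the timeline bars in Figure 3 cannot be read.

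**Assumed.** s is the seasonal shift between half-years, in SD units; the protocol gives none. h is the share of hospitalised children sampled in the same half-year as the community-pneumonia children, all of whom are taken to fall in one half-year.

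**The plan's own figure.** n = 2(1.960 + 1.282)² / 0.505² = 82.4, rounded up to 83. It reproduces, with power 90.2% at 83. The sample size is not in question here.

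**Bias and type I error.** With no true group effect, the expected difference in means is b = s(1 − h). The mixture of seasons widens the hospital group's variance to 1 + s²h(1 − h), so SE = √[(2 + s²h(1 − h)) / 83]. The rejection rate is Φ(b/SE − 1.96) + Φ(−b/SE − 1.96).

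- *Even hospital recruitment over 12 months:* h = 0.5.
- *No shared season:* h = 0.
- *Nine months of enrolment:* section 2.4 also has the study complete within 18 months of the start of recruitment. If the 3-month visits must fit inside that limit, enrolment of the hospitalised group lasts about 12 − 3 = 9 months. Starting straight after a six-month community window, 3 of those 9 months repeat community calendar months, so h = 1/3.

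| Assumed s (SD) | h = 0.5: b, type I | h = 1/3: b, type I | h = 0: b, type I |
|---|---|---|---|
| 0.1 | 0.05, 6.2% | 0.07, 7.1% | 0.10, 9.9% |
| 0.2 | 0.10, 9.8% | 0.13, 13.7% | 0.20, 25.2% |
| 0.3 | 0.15, 16.1% | 0.20, 24.9% | 0.30, 48.9% |
| 0.505 | 0.25, 36.0% | 0.34, 57.1% | 0.505, 90.2% |

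Example for s = 0.3, h = 0: SE = √(2/83) = 0.155, b/SE = 1.93, and Φ(−0.03) is about 49%.

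**What adjustment costs.** Let R² be the squared correlation between group and half-year. With equal groups, the pooled share in the community half-year is p = (1 + h)/2 and R² = [(1 − h)/4]² / [0.25 p(1 − p)].

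- *h = 0.5:* R² = 0.0156/0.0469 = 0.33. The requirement becomes 82.4/(1 − 0.333) = 123.6, or 124 per group. Power at 83 is Φ(0.505√(83 × 0.667/2) − 1.96), about 76%.
- *h = 1/3:* R² = 0.0278/0.0556 = 0.50. The requirement is 82.4/0.5 = 164.8, or 165 per group. Power at 83 is about 63%.
- *h = 0:* R² = 1. Season and group are aliased and no model can separate them.

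**The case against.** **The limitation is disclosed and has a cause.** Section 2.4 names seasonal confounding and explains sequential recruitment by budget, and 2.17.1.1 lists one research nurse and one field research assistant. That explains why the settings cannot run in parallel. It does not explain leaving the hospitalised group unpaced or the primary test unadjusted.

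**Details may sit elsewhere.** Section 2.9 is a summary, a detailed SAP is promised, and Figure 4 is not shown. Secondary or sensitivity adjustment for month may well be planned, and its absence here is no fault. One could infer that the season-spread healthy samples are used for no correction at all; with those sources unseen, the protocol does not support that. What stands is that the protocol itself fixes an unadjusted primary test, and that no SAP can restore overlap that recruitment did not provide.

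**Different period is not different season.** A reader might infer that group and season are wholly confounded, so that 25%, 49% and 90% are the expected error rates. A hospital phase of about 12 months would pass through the community season again, and the word most leaves room for some later community recruitment. Those figures are the no-overlap end of the range.

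**Speed of hospital recruitment.** Section 2.15.1 expects about 500 pneumonia admissions a year, and 92/(500/12) = 2.2 months might suggest that the hospitalised group fills in a single season. The 500 rests on a definition the protocol calls broader than its own and is not stated to be limited to ages 12-24 months. If 25-50% were eligible and enrolled (assumed), 92 children would take about 4-9 months. The 2.2 months is a floor, not a forecast.

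**Case-control comparison.** It is tempting to say that this comparison is confounded in the same way. Cases and controls are recruited at one hospital in one phase, nothing says controls are filled first, and the confounder list in 2.9.2 is open-ended. It is exposed only if the hospitalised group fills faster than the cases.

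**Conclusion.** The point holds for primary objective 2. The protocol recognises seasonal variation, but its remedy does not reach the community-pneumonia group, nothing makes the hospitalised group cover the same months, and the primary test makes no allowance for season.

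The size depends on two unknowns: the seasonal shift, for which no figure is given, and the seasonal overlap, which the plan does not secure. For assumed shifts of 0.2, 0.3 and 0.505 SD, type I error is about 10%, 16% and 36% with even 12-month hospital recruitment, and about 25%, 49% and 90% with no overlap. The largest shift equals the whole planned effect and is shown as an upper illustration only. The 12-month case is the favourable end, since fitting the 3-month visits within 18 months would reduce the overlap.

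Healthy versus hospitalised is partly protected: healthy sampling reaches all seasons, but it is weighted to the first six months and is also tested without adjustment. The case-control comparison is less affected.

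**What to change.** 1. **Section 2.4:** spread enrolment of the hospitalised group evenly across the hospital phase, leaving room for the 3-month visit. The aim is that it covers the calendar months in which community-pneumonia children were sampled and overlaps the cases. State the expected overlap.
2. **Section 2.9.1:** replace the unadjusted t-test with a linear model of group plus calendar season (month as sine and cosine terms, or half-year). Add season to the confounders named in 2.9.2.
3. **Sensitivity analysis:** repeat the comparison in children sampled in the same calendar months.
4. **Return visits already planned:** where feasible, also enrol community-pneumonia children who present, without a fixed quota. Visits every 3-4 weeks for six months give only about 7-9 days, and acute presentations cannot be scheduled.

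**Cost.** The hospitalised group fills more slowly, and precision falls. With half overlap, season adjustment takes power at 83 per group from about 90% to about 76% (124 per group would restore 90%). If enrolment lasts only nine months, power is about 63%. The protocol should state this loss. Item 2 alone is not enough: without overlap the model cannot separate season from group, so item 1 is needed. Season terms also correct only for recurring season; drift between the two calendar periods would remain and should be listed as a limitation.

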2.5 Sample size and calculations

There is no established method for sample size calculation in resistome studies; we use an approach for microbiome studies [25]. Differences in gut plasmidome composition have been detected with 41 participants per group [26], but NPR has a lower biomass than gut resistome, therefore the resistome is likely to be less diverse, with a lower relative abundance of ARGs. NPR analysis 3.5 years post-antibiotic exposure in a cluster-randomised trial of mass-azithromycin administration shows a trend toward decreased NPR diversity (p = 0.07) in azithromycin clusters when compared to placebo clusters, with just 25 samples per group (unpublished data).

We have used the measured difference in relative abundance of a specific macrolide ARG (ermX) 3.5 years after mass-azithromycin administration (unpublished data) as a medium effect size that maybe clinically relevant (Δ = 0.505). Using the approach for microbiome studies, accepting 90% power and 5% type I error (95% confidence interval),

NP Resistome Study

Version 5.0 21/05/2025

Page 15 of 30

we've calculated that we will require a sample size of 83 participants in each group to detect this effect size, using the formula $n=2(Z_{1-\alpha/2}+Z_{1-\beta})^2/\Delta^2$ [25].

In total we aim to recruit 350 study participants: 83 healthy community participants, 92 participants with pneumonia in the community, 92 participants admitted to hospital with pneumonia and 83 participants re-admitted to hospital with pneumonia. Study groups with a sample size of 92 participants permit a 10% loss to follow up.

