2.0 Methodology

2.1 Study design

This is a multi-site, extended case-control study with a preliminary cohort component to assess the evolution of the NPR under selective pressure of antibiotic use and hospital admission for pneumonia in children aged 12-24 months in Malawi. The study will be led by the PhD student, [name], as a PhD fellowship.

NP Resistome Study

Version 5.0 21/05/2025

Page 10 of 30

In the preliminary cohort component, healthy children in the community will have a NPS collected at the first study visit, to determine the baseline community resistome through metagenomic sequencing (see Figure 1).

To assess the impact of oral antibiotics on the NPR, children presenting with pneumonia to community healthcare clinics, Ndirande and Gateway Primary Care Centre (GPCC), will have a NPS collected at the first study visit and 3-months post-recruitment, to determine the antibiotic-exposed resistome through metagenomic sequencing (see Figure 1).

To understand the impact of broad-spectrum intravenous antibiotics and exposure to a hospital environment on the NPR, children hospitalised with pneumonia (without any hospital admission 6 months prior) to Queen Elizabeth Central Hospital (QECH) will have a NPS collected at the first study visit, discharge and 3-months post-recruitment to determine a hospital-acquired resistome through metagenomic sequencing (see Figure 1).

[figure not shown]

Figure 1. Preliminary cohort component of the study. The yellow diamonds represent the key samples groups for NPR comparison.

The case-control component of the study will examine whether a hospital acquired NPR is associated with adverse health outcomes, specifically re-admission to hospital with pneumonia. Children hospitalised to QECH with pneumonia (without admission 6 months prior), who are not re-admitted within 3 months will form the control group (see Figure 2); these participants will have a NPS will be collected at the first study visit (within 24 hours of admission to hospital), discharge from hospital and 3-months post-recruitment to assess for a hospital-acquired resistome. Those hospitalised within the preceding 6 months will be

NP Resistome Study

Version 5.0 21/05/2025

Page 11 of 30

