2.15.5 Failure of long read metagenomic sequencing

Preliminary laboratory work for this study was performed on small numbers of NPS in a UK laboratory setting, with varying yields of long-read DNA following metagenomic sequencing; this was attributed to use of sequencing equipment (MinION flow cells) beyond their recommended storage period. There is a chance that DNA extraction and long-read sequencing will not yield the expected results in a different laboratory setting. Prior to study recruitment, trials of DNA extraction and long-read sequencing will be performed on NPS and a laboratory reference standard, the ZymoBIOMICS microbial community standard, to ensure reliability and reproducibility of sequencing results.

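### The 92 hospital children allow for 10% loss to follow-up but not for re-admitted children, who cannot be controls; the two 18-month statements also need reconciling

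*Protocol*

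**What the plan says.** Section 2.5 of the protocol calculates 83 per group, "accepting 90% power and 5% type I error (95% confidence interval"), and takes a standardised difference from unpublished data "as a medium effect size that maybe clinically relevant (Δ = 0.505"). It enrols 83 healthy children, 92 with pneumonia in the community, 92 hospitalised and 83 re-hospitalised. The only allowance for loss is this: "Study groups with a sample size of 92 participants permit a 10% loss to follow up".

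Section 2.1 defines the controls for the case-control comparison as hospitalised children "who are not re-admitted within 3 months will form the control group". They are swabbed at admission, at discharge and 3 months after recruitment. Cases have one visit, at re-admission.

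Section 2.15.1 says that no re-admission data exist for pneumonia in the region. It works through a scenario with the severe-anaemia figure of 18% over 6 months. Sections 2.1 and 2.15.1 plan a 4-week audit of re-admissions before recruitment, to inform the sample size.

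Section 2.4 describes the study as "with participant recruitment over an 18-month period", with community children recruited before hospital children. It later states: "The study will be completed within 18 months of the start of recruitment". An earlier finish is allowed if targets are met and all samples are in before then.

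**The concern.** Loss to follow-up and re-admission are different losses. A re-admitted child may be followed up completely and still cannot be a control. Section 2.5 counts only the first loss, so the control group defined in section 2.1 is expected to fall short of the 83 on which the stated power rests. The comparison affected is the one between re-admitted and non-re-admitted children, which addresses part of the third primary objective.

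The timing statements raise a second question. A control can be confirmed, and the 3-month swab taken, only 3 months after enrolment. If recruitment lasts 18 months and the study is complete by month 18, a hospital child enrolled in the last 3 months has no room for either. The 3-month swab also serves the persistence part of the same objective.

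**Working it through.** **Inputs.** From section 2.5: two-sided α = 0.05, power 0.90, Δ = 0.505, 92 hospital children, 83 cases, 10% loss to follow-up. From section 2.1: re-admission within 3 months excludes a child from the controls. From section 2.15.1: 18% re-admission over 6 months and about 500 hospital admissions with pneumonia a year, both used there as working figures. The conversion of 18% to a 3-month risk is an assumption, so a range is shown.

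**1. The plan's own figures.** n = 2(1.960 + 1.282)²/0.505² = 82.4, rounded up to 83. This agrees with section 2.5. After the stated loss, 92 × 0.9 = 82.8, which is 83 to the nearest child. The two-sample t-test power for 83 against 83 is 89.9% (normal approximation 90.2%). The stated figures reproduce.

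**2. Three-month re-admission risk r.** At constant risk, r = 1 − (1 − 0.18)^0.5 = 0.0945, about 9.4%. If nearly all re-admissions in the 6 months fall in the first 3, r approaches 18%.

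**3. Expected controls and power.** Controls = 92 × 0.9 × (1 − r), treating the two losses as independent. Power is for a two-sided t-test at Δ = 0.505 against 83 cases.

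| r | Controls | Power |
|---|---|---|
| 0 | 82.8 | 89.8% |
| 2% | 81.1 | 89.5% |
| 5% | 78.7 | 89.1% |
| 9.4% | 75.0 | 88.3% |
| 18% | 67.9 | 86.6% |

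The normal approximation gives 88.7% at r = 9.4% and 87.0% at r = 18%. If the two losses fall on different children, the controls are 92 × (0.9 − 0.0945) = 74.1 and 92 × (0.9 − 0.18) = 66.2, which changes little.

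**4. When 83 is still reached.** With no loss to follow-up, 83 controls remain as long as r ≤ 1 − 83/92 = 9.8%. At r = 9% (so 92 × 0.91 = 83.7), loss to follow-up must stay below 1 − 83/83.7 = 0.9%. At the planned 10% loss there is no slack at all.

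**5. Enrolment that would restore 83.** N = 83/(0.9 × (1 − r)) gives 102 at r = 9.4% and 113 at r = 18%.

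**6. The 18-month statements.** Recruitment over 18 months and completion by month 18 leave 18 − 18 = 0 months of follow-up for the last child enrolled, against the 3 needed. How many hospital children this touches depends on when the 92 are filled. At 500 admissions a year, if every child were enrolled, it takes 92/500 × 12 = 2.2 months. At half that inflow it takes 4.4 months, and at a quarter 8.8. Section 2.15.1 notes that the 500 rests on a broader pneumonia definition, so the slower figures are plausible. If the group fills 3 months or more before the end, no child is affected.

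**The case against.** The strongest reply is that the effect is small and the rate hypothetical. The fall from 89.9% to 88.3% is 1.6 points, well inside the uncertainty of an effect size taken from one gene in unpublished data. The 18% comes from severe anaemia, which the study excludes, and the planned audit is meant to revise the sample size. All of this stands and limits the size of the point. It does not remove it: section 2.5 states a margin with no term for an exclusion that section 2.1 makes by definition, and the audit result has no place in the calculation until such a term is added.

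A reader might infer more than the protocol supports:

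- **That 83 controls are out of reach.** They are not. Low re-admission together with loss well under 10% would still give 83.
- **That the last 3 months of hospital enrolment are certain to be lost.** No text says that the 92 are enrolled up to the final month. The timeline shading in Figure 3 cannot be read here, and its rows cover recruitment together with data collection, so the 18 months may be meant to include follow-up. The early-finish clause mentions collection of all samples, but it applies only when the study ends before month 18, so it does not settle the wording.
- **That re-admission also shrinks the persistence analysis.** Only the control definition excludes re-admitted children. They stay in the hospital group, with a 3-month swab planned and admissions recorded at that visit.
- **That sequencing failure should be added as an expected loss.** Section 2.15.5 reports "varying yields of long-read DNA following metagenomic sequencing", but attributes this to expired flow cells and plans trials before recruitment. It gives no failure rate. The 83-child groups have a single visit and need no follow-up allowance.

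**Conclusion.** The point holds as a planning-margin gap of modest size. At the planned 10% loss, any re-admission takes the expected controls below 83. On the protocol's own working rate, about 75 controls are expected, or 68 if re-admissions come early. Power against 83 cases is about 88%, or 87%, instead of 90%. These figures rest on a re-admission rate borrowed from severe anaemia, on constant risk for the 75, on independence of the two losses, and on the 83 cases being recruited in full.

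The two 18-month statements cannot both be carried out literally if hospital enrolment runs to the end. This is a wording conflict to be reconciled. No expected loss can be attached to it, because the protocol gives no accrual pattern and the number affected may be zero.

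**What to change.** 1. In section 2.5, add the re-admission exclusion to the calculation for the case-control comparison. State the expected evaluable controls (about 75, range down to 68) and the power (about 88%, down to 87%), with the assumed 3-month risk. Say that both will be updated with the re-admission rate from the 4-week audit.
2. If 83 controls are to be kept, enlarge the hospital group by the formula in step 5 of the working. That means 10 more children at 9.4% (102 − 92) or 21 more at 18% (113 − 92), each with three planned swabs. Restating the power is cheaper and is enough, given the small loss.
3. In section 2.4, define study completion as the last 3-month visit. Alternatively, close enrolment of the hospital (control) group at least 3 months before study end and leave the single-visit case group open.

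Items 1 and 3 are changes of protocol wording. The cost is a slightly lower stated power and either a later formal end of study or a shorter enrolment window for one group.
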